7.1.2.7 Definitions of Measurable and Non-measurable Lesions and Disease

See Section 12.3. Measurable and Non-measurable disease is defined by RECIST 1.1.

7.1.2.8 Definition of Target, Non-Target Lesions

See Section 12.3.

7.1.2.9 New Lesions

See Table 7 for a description of the determination of progression based on the presence of new lesions.

Note: The appearance of a new lesion does not by itself satisfy the criteria for confirmed progressive disease. Rather, the tumor burden imposed by the new lesion must be evaluated within the context of the total tumor burden (pre-existing plus new lesions). Confirmation of progression in Target lesions, Non-target (non-bone) lesions, and Bone lesions require 2 assessment time points. The first of these (TP1) must occur at Week 12 or later with the second (TP2) occurring at least 6 weeks later. Progression declared at TP1 remains unconfirmed unless TP2 demonstrates continuing or worsening progression as described in Section 7.1.2.11. See section 12.3 for more information regarding soft tissue disease.

7.1.2.10 Method of Tumor Response Assessment

If, due to a radioisotope shortage, your imaging facility is unable to perform a Technetium-99 (Tech-99) bone scan at a protocol-specified time point, then the following scanning options may be used:

- Full body CT
- Full body MRI
- Fluoride PET

7.1.2.11 Disease Progression Criteria

At each disease assessment, progression (PD) will be determined using the criteria in Table 7. For treatment guidance, and for the purpose of efficacy assessments, confirmation PD is required. The

rationale for confirmation of PD is based on recommendations from the Prostate Cancer Working Group 2 (PCWG2): “Therapy may be prematurely discontinued if outcome measures do not reflect disease status accurately. As noted, bone scans in particular, are relatively insensitive in the early follow-up period. Consideration of drug pharmacodynamics is also important. For example, a successful vaccination might produce a lymphocytic infiltrate in a tumor mass that would transiently increase its size giving the false impression of worsening disease. To avoid misinterpreting these early results, PCWG2 asserts that any post-treatment change in disease status, be it favorable or unfavorable, be confirmed using a second assessment at a later time point.”(32)

Therefore, confirmation of progression in PSA requires 3 assessment time points. Confirmation of progression in Target lesions, Non-target (non-bone) lesions, and Bone lesions requires 2 assessment time points. The first of these (TP1) must occur at Week 12 or later with the second (TP2) occurring at least 6 weeks later. Progression declared at TP1 remains unconfirmed unless TP2 demonstrates continuing or worsening progression as described below:

PSA: The first PSA at week 12 or after must demonstrate a $\geq 25\%$ increase and ≥ 2 ng/ml increase above nadir (TP1). PSA progression at TP1 remains unconfirmed unless followed by a confirmed rising trend in 2 subsequent PSA values. PSA at TP2 must be $>$ PSA at TP1.

Note: Since PSA values obtained between week 1 and week 12 are not considered when determining progression, they cannot be used as nadir.

- Target and Non-target (non-bone) lesions: Use RECIST 1.1 for progression, with additional requirements that progression at first assessment (TP1) be confirmed by a second scan 6 or more weeks later. See Section 12.3 for information about soft tissue disease.
- Bone lesions: Assessment at TP1 must demonstrate the appearance of 2 or more new lesions. Progression at TP1 remains unconfirmed unless the TP2 assessment demonstrates the appearance of an additional 2 or more lesions when compared to TP1. After TP1 the appearance of 2 or more new lesions need to be confirmed with an additional scan 6 or more weeks later. The subsequent scan must show persistence of previous lesions or additional new lesions.

Note: If unconfirmed progression noted at TP1 is not confirmed at TP2, the next assessment time point after TP1 that meets the criteria for progression is treated as TP1.

Table 7: Definition of Disease Progression

Disease Parameter	Unconfirmed Progression Time Point 1 (TP1)	Confirmed Progression	Date of Progression

PSA (requires 2 measurements) ^a	$\geq 25\%$ increase and ≥ 2 ng/ml increase above the nadir (Ignore PSA prior to week 12)	PSA continues to climb 3 weeks after the first progression	TP1
Target Lesions (CT/MRI) Section 12.3 for soft tissue disease assessment	$\geq 20\%$ increase in the sum of diameters of target lesions. The sum must also demonstrate an absolute increase of at least 5mm. Or the appearance of one or more new lesions \geq Week 12	TP2 Sum of diameters of TP2 \geq Sum of diameters of TP1 Confirmation of radiographic progression is not required for soft tissue after Week 12	TP1
Non-Target Lesions (non-bone) (CT/MRI)	Unequivocal progression of existing non-target lesions (The appearance of one or more new lesions is also considered progression) See Section 12.3 for more information.	TP 2 Continued progression of non-target lesions Confirmation of radiographic progression is not required for soft tissue after Week 12	TP1
Bone (Bone scan/X-ray)	Appearance of ≥ 2 new lesions	TP2 Appearance of ≥ 2 new lesions compared to TP1 After Week 12 the appearance of two new lesions need to be confirmed 6 or more weeks later. The confirmatory scan must show	TP1

		
persistence of previous lesions or additional new lesions
	
Clinical Deterioration	
Clinical Deterioration at any time (defined as Persistent decrease in performance status (eg, lasting for more than 14 days) of at least 2 points from baseline, attributable to disease progression)
 
Any time
	Date of Clinical Deterioration	

a Since PSA values obtained between week 1 and week 12 are not considered when determining progression, they cannot be used as nadir.

Definition of PSA and Radiographic Stability. Neither response nor progression.

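### Read literally, Table 7's target-lesion row can confirm a Week-12 progression after the new soft-tissue lesion that triggered it has disappeared, against 7.1.2.9 and 7.1.2.11

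*Combined protocol and SAP*

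**What the plan says.** Section 7.1.2.11 makes Table 7 the working definition: "At each disease assessment, progression (PD) will be determined using the criteria in Table 7". The target-lesion row reads as follows.

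- **TP1:** at least a 20% "increase in the sum of diameters of target lesions", together with the 5 mm minimum, or a new lesion at Week 12 or later: "The sum must also demonstrate an absolute increase of at least 5mm. Or the appearance of one or more new lesions".
- **TP2:** the sum of diameters must be at least the "Sum of diameters of TP1". New lesions are not mentioned, and equality is enough.
- **Date of progression:** TP1.
- **Waiver:** "Confirmation of radiographic progression is not required for soft tissue after Week 12".

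The non-target (non-bone) row also counts a new lesion at TP1, but its TP2 cell asks for continued progression of the non-target lesions.

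Section 7.1.2.9 says that a new lesion is not by itself confirmed progression, and that "the tumor burden imposed by the new lesion must be evaluated within the context of the total tumor burden (pre-existing plus new lesions". For how this is determined it refers the reader back: "See Table 7 for a description of the determination of progression based on the presence of new lesions". The text of 7.1.2.11 leaves a TP1 progression unconfirmed unless TP2 shows that it is continuing or getting worse. Section 5.8 requires discontinuation for confirmed radiographic progression and cites Table 7.

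**The concern.** Confirmation exists so that a change seen once does not take a man off treatment if it later proves not to be progression. When TP1 rests on a new lesion, TP2 should look at that lesion. The target row looks at something else: whether the target sum has held or grown. A man whose targets never progressed and whose new lesion has gone would be recorded as confirmed, with progression dated to Week 12.

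Week 12 is the first scheduled on-treatment scan for every subject (7.1.2.6), so this is where the rule first applies. At stake are:

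- mandatory discontinuation under 5.8;
- through that, loss of later retreatment;
- the move to telephone survival follow-up, which 7.1.5.4.1 ties to confirmed progression.

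**Working it through.** The plan gives no figure to reproduce. The check applies the stated rules to the same pair of scans.

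**1. One case, three rules.** TP1 at Week 12 is a new soft-tissue lesion only. At TP2 that lesion is gone, targets are unchanged and non-target lesions are not progressing.

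- Target row, read literally: TP2 sum equals TP1 sum, so confirmed.
- Non-target row: no continued non-target progression, so not confirmed.
- 7.1.2.9 and the text of 7.1.2.11: total burden has fallen and nothing is continuing or worsening, so not confirmed.

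By contrast, the bone row's confirmation looks at the lesions themselves: further new lesions or, after Week 12, persistence or additions.

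**2. Worked sizes (assumed, not patient data).** Target sum 50 mm at nadir and at TP1; new lesion 15 mm at TP1 and 0 at TP2. Total burden at TP1 is 50 + 15 = 65 mm.

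| Target sum at TP2 | Literal row (TP2 ≥ 50) | Total burden (TP2 ≥ 65) |
|---|---|---|
| 50 mm | confirmed | 50 < 65, not confirmed |
| 51 mm | confirmed | 51 < 65, not confirmed |
| 49 mm | not confirmed | 49 < 65, not confirmed |

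The fault needs targets that are unchanged or slightly larger. Any shrinkage fails TP2.

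**3. Is including the new lesion enough?** Let T be the target sum at TP1 (assumed equal to nadir), n the new lesion at TP1 (gone at TP2) and d the whole-millimetre change in targets.

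- Literal row confirms if d ≥ 0.
- Inclusive sum confirms if T + d ≥ T + n, that is d ≥ n.
- Targets progress in their own right if d ≥ max(5, 0.2T).

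The table counts the values of d from 0 up to just below that threshold at which each rule confirms.

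| T (threshold) | Literal | Inclusive, n = 5 | n = 10 | n = 12 | n = 20 |
|---|---|---|---|---|---|
| 20 mm (5) | 5 of 5 | 0 | 0 | 0 | 0 |
| 50 mm (10) | 10 of 10 | 5 | 0 | 0 | 0 |
| 80 mm (16) | 16 of 16 | 11 | 6 | 4 | 0 |

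The literal column is complete by construction, because every d ≥ 0 confirms. If shrinking targets are counted too (T = 50, d from −9 to 9), it is 10 of 19. These counts illustrate the rule and do not measure frequency. Their one use is to show that including the new lesion still leaves a gap when the lesion is small relative to the targets, so a separate clause on a vanished lesion is needed.

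**4. Timing.** Dose 4 falls at 3 × 3 = 9 weeks, or 3 × 4 = 12 weeks if each interval is lengthened by one week. TP2 falls between Week 18 (12 + 6) and the scheduled Week-24 scan. Confirmation therefore comes 9 to 15 weeks after dose 4, or 6 to 12 weeks with the lengthened intervals.

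**The case against.** The strongest reply is that the protocol already contains the right rule. The TP2 cell says only sum of diameters; the restriction to target lesions comes from the row label and the TP1 cell. Read with 7.1.2.9, the sum covers pre-existing and new lesions, and most of the problem goes. That stands as the sensible reading. But 7.1.2.9 sends the reader to Table 7, while 7.1.2.11 and 5.8 also rely on the table, and the table does not carry the rule. Nor does this reading settle which row governs or close the small-lesion gap.

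The scope is also narrow. If the post-Week-12 waiver holds, only a TP1 at the Week-12 scan is affected. A later TP1 is affected only if the confirmation text in 7.1.2.6, 7.1.2.9 and 7.1.2.11 overrides the waiver. Section 5.8 lets a clinically stable or improved man continue after a prior contact, and a man with stable targets and a resolved lesion is a natural candidate.

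Three stronger readings are tempting, and the documents do not support them.

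- A reader might infer that 7.1.2.6 predicts this very pattern. Its flare text describes swelling at existing disease sites, not new lesions that come and go.
- A reader might infer that 7.1.5.2 directly bars such men from retreatment. It is judged at 12 weeks, accepts stability or response by PSA or imaging, and does not cite TP2. The loss runs only through discontinuation under 5.8.
- A reader might add the reverse error, a growing new lesion left unconfirmed because targets shrank. The reset note ("the next assessment time point after TP1 that meets the criteria for progression is treated as TP1") and the waiver make that mostly a later date, so it is not relied on.

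**Conclusion.** The conflict is real but small. Under its literal wording, the target row confirms progression in a case where 7.1.2.9, the text of 7.1.2.11 and the non-target row would not. The result rests on reading the TP2 sum as the target-lesion sum, and on a Week-12 TP1 triggered only by a new soft-tissue lesion that is gone at TP2, with targets unchanged or larger.

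The consequence is possible mandatory discontinuation, with what follows from it for retreatment and follow-up. On the timings above, first-course dosing is complete before confirmation. The definitions of the endpoints listed in 8.1 (PSA response, PSA progression-free survival, objective response and overall survival among them) are untouched, and radiographic progression-free survival is not listed. How often this would happen cannot be derived: the documents do not say how many men would have target lesions and a new soft-tissue lesion at Week 12. Severity is low: a wording correction to a rule that is in operation.

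**What to change.** In Table 7, state three things:

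1. When TP1 rests on a new soft-tissue lesion, the sums compared at TP1 and TP2 both include the new lesion or lesions, in line with 7.1.2.9.
2. A new lesion that is absent at TP2, with no target or non-target progression, is not confirmed progression. This brings every count in the illustration to zero.
3. Which row governs a new soft-tissue lesion.

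Record on the tumour-assessment form which criterion triggered TP1. The cost is Table 7 wording and one form field, with no added scans.

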7.1.2.12 Disease Response Criteria

PSA decrease of at least 50%.

Radiographic Response will be determined using RECIST 1.1.(33)

[See Section 12.3.](#)

7.1.2.13 Tumor Tissue Collection and Correlative Studies Blood Sampling

For all subjects, we will request the tumor block or 10 unstained slides from the initial diagnosis, such as biopsy or from radical prostatectomy. In addition, for subjects with a biopsy accessible metastatic deposit, we will collect 6 tissue cores. Blood (100 mL) will be collected just prior to pembrolizumab at each dose. See Appendices 12.4 and 12.5 for additional details.

7.1.2.14 Normal Tissue Collection

Normal tissue can be collected from any non-tumor source, including whole blood (20 mLs), normal tissue collected during study biopsy or during non-study procedure (surgical discard), skin, or saliva. Our plan is to collect whole blood on patients (20 mLs) during screening, treatment, or non-treatment follow-up. However, if non-cancer tissue has already been collected (study biopsy or other procedure) and is available, we will use that tissue in lieu of an additional blood draw.

7.1.3 Laboratory Procedures/Assessments

Details regarding specific laboratory procedures/assessments to be performed in this trial are provided below. Please contact the sponsor for details concerning the total amount of blood/tissue to be drawn/collected over the course of the trial (from pre-trial to post-trial visits), including approximate blood/tissue volumes drawn/collected by visit and by sample type per subject.

7.1.3.1 Laboratory Safety Evaluations (Hematology, Chemistry and Urinalysis)

Laboratory tests for hematology, chemistry, urinalysis, and others are specified in Table 8. Please contact the sponsor for details concerning the total amount of blood/tissue to be drawn/collected over the course of the trial (from pre-trial to post-trial visits), including approximate blood/tissue volumes drawn/collected by visit and by sample type per subject can be found in Sections 12.4 and 12.5.

Table 8 Laboratory Tests

Hematology	Chemistry	Urinalysis	Other
Hematocrit	Albumin	Blood	PT (INR)
Hemoglobin	Alkaline phosphatase	Glucose	aPTT
Platelet count	Alanine aminotransferase (ALT)	Protein	Total triiodothyronine (T3)
WBC (total and differential per institutional standard)	Aspartate aminotransferase (AST)	Specific gravity	Free tyroxine (T4)
Red Blood Cell Count	Carbon Dioxide ‡		Thyroid stimulating hormone (TSH)
Absolute Neutrophil Count	(CO ₂ or bicarbonate)		C Reactive Protein
	Calcium		Blood for correlative studies
	Chloride		Lactate Dehydrogenase (LDH)
	Glucose		
	Creatinine		
	Potassium		
	Sodium		
	Total Bilirubin		
	Direct Bilirubin (If total bilirubin is elevated above the upper limit of normal)		
	Total protein		
	Blood Urea Nitrogen		
	Blood Urea Nitrogen		

Laboratory tests for screening or prior to retreatment should be performed within 28 days prior to the first dose of treatment. After Cycle 1, pre-dose laboratory procedures can be conducted up to 72 hours prior to dosing. Results must be reviewed by the investigator or qualified designee and found to be acceptable prior to each dose of trial treatment.

7.1.3.2 Pharmacokinetic/Pharmacodynamic Evaluations

7.1.3.2.1 Blood and Tissue Collection for Correlative Work and Serum Pembrolizumab

See Appendices 12.4 and 12.5 for details.

PK data will not be done for this study. PK analysis has been done on previous studies with pembrolizumab. The PK is not changed by chemotherapy or other concomitant medications. This is not surprising considering it is an antibody.

7.1.3.2.2 Blood Collection for Anti-Pembrolizumab Antibodies

Sample collection, storage and shipment instructions for blood samples are provided in Section 12.4.

7.1.4 Other Procedures

7.1.4.1 Withdrawal/Discontinuation

When a subject discontinues/withdraws prior to trial completion, all applicable activities scheduled for the final trial visit should be performed at the time of discontinuation. Any adverse events which are present at the time of discontinuation/withdrawal should be followed in accordance with the safety requirements outlined in Section 7.2 - Assessing and Recording Adverse Events. After discontinuing treatment following assessment of CR, these subjects should return to the site for a Safety Follow-up Visit (described in Section 7.1.5.3.1) and then proceed to the Follow-Up Period of the study (described in Section 7.1.5.4).

7.1.4.2 Blinding/Unblinding. This is an open label study.

7.1.5 Visit Requirements

Visit requirements are outlined in Section 6.0 - Trial Flow Chart. Specific procedure-related details are provided above in Section 7.1 - Trial Procedures.

7.1.5.1 Screening

7.1.5.1.1 Screening Period

The screening period begins at the time of consent and lasts 28 days. During this time, subjects will undergo imaging studies (CT and NM bone scan) and blood work to ensure they are suitable candidates. They will also undergo a biopsy if they have a lesion amenable to biopsy. Assessments

completed prior to consenting for clinical purposes (such as CT or Bone scans, or blood work) will not be required to be repeated if they are within the 28 day screening period.

7.1.5.2 Treatment Period

All subjects will receive four doses of pembrolizumab, unless they withdraw from the study. No official assessments of response will occur during these treatments, even though the PSA will be drawn. Those subjects who have stable disease or a disease response by PSA or imaging at 12 weeks can go on to receive additional treatments until disease progression. Those subjects who have clearly progressive disease after the initial four treatments will not be retreated with pembrolizumab.

7.1.5.3 Post-Treatment Visits

7.1.5.3.1 Safety Follow-Up Visit

The mandatory Safety Follow-Up Visit should be conducted approximately 30 days after the end of treatment visitor before the initiation of a new anti-cancer treatment, whichever comes first. All AEs that occur prior to the Safety Follow-Up Visit should be recorded. Subjects with an AE of Grade > 1 will be followed until the resolution of the AE to Grade 0-1 or until the beginning of a new anti-neoplastic therapy, whichever occurs first. SAEs that occur within 90 days of the end of treatment or before initiation of a new anti-cancer treatment should also be followed and recorded.

7.1.5.4 Follow-up Visits

Subjects who discontinue trial treatment for a reason other than disease progression will move into the Follow-Up Phase and should be assessed every 12 weeks (84 ± 7 days) by radiologic imaging to monitor disease status. Every effort should be made to collect information regarding disease status until the start of new anti-neoplastic therapy, disease progression, death, end of the study or if the subject begins retreatment with pembrolizumab as detailed in Section 7.1.5.2. Information regarding post-study anti-neoplastic treatment will be collected if new treatment is initiated.

Subjects who are eligible to receive retreatment with pembrolizumab according to the criteria in Section 7.1.5.2 will move from the follow-up phase to the Second Course Phase when they experience disease progression. Details are provided in Section 6.2 – Trial Flow Chart for Retreatment. Of note, it is possible to be retreated indefinitely.

7.1.5.4.1 Survival Follow-up

Once a subject experiences confirmed disease progression or starts a new anti-cancer therapy, the subject moves into the survival follow-up phase and should be contacted by telephone every 12 weeks to assess for survival status until death, withdrawal of consent, or the end of the study, whichever occurs first.

7.2 Assessing and Recording Adverse Events

An adverse event is defined as any untoward medical occurrence in a patient or clinical investigation subject administered a pharmaceutical product and which does not necessarily have to have a causal relationship with this treatment. An adverse event can therefore be any unfavorable and unintended sign (including an abnormal laboratory finding, for example), symptom, or disease temporally associated with the use of a medicinal product or protocol-specified procedure, whether or not considered related to the medicinal product or protocol-specified procedure. Any worsening (i.e., any clinically significant adverse change in frequency and/or intensity) of a preexisting condition that is temporally associated with the use of the Merck's product, is also an adverse event.

For laboratory abnormalities, the criteria for determining whether an abnormal test finding should be reported as an adverse event are as follows:

- Test result is associated with accompanying symptoms, and/or
- Test result requires additional diagnostic testing or medical/surgical intervention, and/or
- Test result leads to a change in study dosing outside of protocol-stipulated dose adjustments or discontinuation from the study, significant additional concomitant drug treatment, or therapy, and/or
- Test result is considered to be an adverse event by the Investigator

Merck product includes any pharmaceutical product, biological product, device, diagnostic agent or protocol-specified procedure, whether investigational (including placebo or active comparator medication) or marketed, manufactured by, licensed by, provided by or distributed by Merck for human use.

Adverse events may occur during the course of the use of Merck product in clinical trials or within the follow-up period specified by the protocol, or prescribed in clinical practice, from overdose (whether accidental or intentional), from abuse and from withdrawal.

Adverse events may also occur in screened subjects during any pre-allocation baseline period as a result of a protocol-specified intervention, including washout or discontinuation of usual therapy, diet, placebo treatment or a procedure.

All adverse events will be recorded from the time the consent form is signed through 30 days following cessation of treatment and at each examination on the Adverse Event case report forms/worksheets. The reporting timeframe for adverse events meeting any serious criteria is described in section 7.2.3.1.

Adverse events will not be collected for subjects during the pre-screening period (for determination of archival tissue status) as long as that subject has not undergone any protocol-specified procedure or intervention. If the subject requires a blood draw, fresh tumor biopsy etc., the subject is first required to provide consent to the main study and AEs will be captured according to guidelines for standard AE reporting.

7.2.1 Definition of an Overdose for This Protocol and Reporting of Overdose to the Sponsor and to Merck

For purposes of this trial, an overdose will be defined as any dose exceeding the prescribed dose for pembrolizumab by 20% over the prescribed dose. No specific information is available on the treatment of overdose of pembrolizumab. In the event of overdose, pembrolizumab should be discontinued and the subject should be observed closely for signs of toxicity. Appropriate supportive treatment should be provided if clinically indicated.

If an adverse event(s) is associated with (“results from”) the overdose of a Merck product, the adverse event(s) is reported as a serious adverse event, even if no other seriousness criteria are met.

If a dose of Merck’s product meeting the protocol definition of overdose is taken without any associated clinical symptoms or abnormal laboratory results, the overdose is reported as a non-serious Event of Clinical Interest (ECI), using the terminology “accidental or intentional overdose without adverse effect.”

All reports of overdose with and without an adverse event must be reported within 24 hours to the Sponsor and within 2 working days hours to Merck Global Safety. (Attn: Worldwide Product Safety; [contact])

